2.6.4 Supportive/sensitivity analyses

N/A

2.7 Analysis of secondary efficacy objectives

All secondary efficacy analysis will be based on the FAS (observed data only).

2.7.1 Secondary endpoints

The secondary efficacy variables are the following:

- proSPI (s, p, i) score at all assessment periods
- saSPI (s, p, i) score at all assessment periods
- Dermatology life quality index (DLQI) score at all assessment periods
- saPASI score at all assessment periods
- Psoriasis Symptom diary at all assessment periods
- correlation between each of proSPI (s, p, i) and DLQI, and proSPI (p, i) and PASI, at all assessment periods

2.7.2 Statistical hypothesis, model, and method of analysis

ProSPI and saSPI

Descriptive statistics of absolute values and change from Baseline at all assessment periods for proSPI (s, p, i) and saSPI (s, p, i) will be presented separately.

The number and percentage of proSPI (p, i) and saSPI (p, i) will be presented by visit and by the following score bands: 0, 1, 2, ..., 9, 10. Graph of reponse distribution of proSPI (p, i) and saSPI (p, i) will be presented by the aforementioned score band at Week 16.

DLQI

The DLQI contains six functional scales (symptoms and feeling, daily activities, leisure, work and school, personal relationships, treatment). Seven scores will be derived from the DLQI: the total score of each of the six dimensions as well as the total score over all items. Details on the calculation of DLQI are given in [Appendix 5.2](#).

For each of the seven scores the percentage change from Baseline at each visit will be derived. Summary statistics will be provided for absolute values as well as for the percentage change by visit.

Number and percentage of patients achieving DLQI status 0 or 1 will be provided by visit.

SaPASI

Absolute value, absolute change and percentage change from Baseline of saPASI score will be summarized by visit. The number and percentage of saPASI score will be presented by body region, symptom, and visit.

Psoriasis Symptom Diary

Descriptive summary statistics will be presented for absolute values and change from Baseline by visit for intensity of pain, itching and scaling separately.

Correlations between scores

Computation of Spearman's correlation coefficient at each post-Baseline visit and graphing of scatterplot at Week 16 will be performed on the following scores:

- between proSPI (s, p, i) and DLQI (total score)

- between proSPI (p, i) and PASI

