2.1.1.3 Baseline and post-Baseline

Baseline data will be defined as the last available non-missing data collected prior to the first study treatment administration. Data collected after first dose of study treatment will be considered as post-Baseline data.

Change from Baseline will only be summarized for patients with both Baseline and post-Baseline unless stated otherwise, and it will be calculated as:

$$\text{post-Baseline value} - \text{Baseline value}$$

Correspondingly, percentage change will be calculated as:

$$100 * (\text{post-Baseline value} - \text{Baseline value}) / \text{Baseline value}$$

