5.2 Calculation of Dermatology Life Quality Index (DLQI)

DLQI contains six functional scales (symptoms and feeling, daily activities, leisure, work and school, personal relationships, treatment). Each question will be answered with the following response: “not at all”, “a little”, “a lot”, “very much”, or “not relevant”. Seven scores will be derived from the DLQI: the score of each of the six dimensions as well as the total score over all items. The higher the score, the more quality of life is impaired.

Scoring

The scoring of each question is as follows:

Table	Score
Very much	3
A lot	2
A little	1
Not at all	0
Not relevant	0
Question unanswered	0
Yes (Question 7: “prevented work or studying”)	3

The DLQI is calculated by summing the score of each question resulting in a maximum of 30 and a minimum of 0. The higher the score, the more quality of life is impaired. The DLQI can also be expressed as a percentage of the maximum possible score of 30.

Meaning of DLQI Scores

- 0-1 = no effect at all on patient's life
- 2-5 = small effect on patient's life
- 6-10 = moderate effect on patient's life
- 11-20 = very large effect on patient's life
- 21-30 = extremely large effect on patient's life

Detailed analysis of the DLQI

The DLQI can be analysed under six headings as follows:

Section	Question	Score
Symptoms and feelings	1, 2	maximum 6
Daily activities	3, 4	maximum 6
Leisure	5, 6	maximum 6
Work and School	7	maximum 3
Personal relationships	8, 9	maximum 6
Treatment	10	maximum 3

The scores for each of these sections can also be expressed as a percentage of either 6 or 3.

Interpretation of incorrectly completed questionnaires

There is a very high success rate of accurate completion of the DLQI. However, sometimes subjects do make mistakes.

1. If one question is left unanswered this is scored 0 and the scores are summed and expressed as usual out of a maximum of 30.
2. If two or more questions are left unanswered the questionnaire is not scored.
3. If question 7 is answered 'yes' this is scored 3. If question 7 is answered 'no' but then either 'a lot' or 'a little' is ticked this is then scored 2 or 1. If "Not relevant" is ticked, the score for Question 7 is 0. If it is answered 'no', but the second half is left incomplete, the score will remain 0.
4. If two or more response options are ticked, the response option with the highest score should be recorded.

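### DLQI change is summarised only as percentage change, which is undefined at a Baseline of 0 and drops those patients score by score, mainly on the sub-scales

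*SAP*

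**What the plan says.** Section 2.7.2 of the SAP treats the DLQI as seven scores: the total and six sub-scales. For the change measure it states: "For each of the seven scores the percentage change from Baseline at each visit will be derived". The planned output is: "Summary statistics will be provided for absolute values as well as for the percentage change by visit". It adds a count: "Number and percentage of patients achieving DLQI status 0 or 1 will be provided by visit". Absolute change from Baseline is not listed for any DLQI score.

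The next paragraph of the same section handles saPASI differently: "Absolute value, absolute change and percentage change from Baseline of saPASI score will be summarized by visit". Change from Baseline is also planned for the SPI components and the symptom diary (2.7.2), and absolute change for PASI (2.6.2).

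The formula follows the words "Correspondingly, percentage change will be calculated as" in section 2.1.1.3. It puts the Baseline value in the denominator and gives no rule for a Baseline of 0.

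Appendix 5.2 shows that 0 can occur. The total is a sum "resulting in a maximum of 30 and a minimum of 0". On the sub-scale maxima: "The scores for each of these sections can also be expressed as a percentage of either 6 or 3". Work and School consists of Question 7 alone, and if 'Not relevant' "is ticked, the score for Question 7 is 0". Section 2.7.3 does not replace missing values of secondary variables.

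**The concern.** A percentage change needs a positive Baseline. The DLQI sub-scales have few score levels, and two of them (Work and School, Treatment) are single items with a maximum of 3. A patient with no impairment in one domain, or for whom the domain does not apply, scores 0 there at Baseline and has no percentage change at any visit.

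These patients are not a random subset. A score of 0 cannot fall, so their change is either zero or a worsening. The only within-patient change summary for a sub-scale therefore covers a sample selected on its own Baseline value.

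There is a second weakness where the Baseline is small but not 0: one or two points become very large percentages, so a few patients can drive the mean.

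At stake is the reading of the DLQI sub-scale change tables in a single-arm study, where change from Baseline carries most of the interpretation. The programmer would also have to improvise a rule for 0.

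**Working it through.** The SAP gives no figure for this point, so there is nothing of its own to reproduce. The check applies its formula and then shows the effect of exclusion under stated assumptions.

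**1. The formula at and near 0** (2.1.1.3): 100 × (post - Baseline) / Baseline.
- Baseline 0, visit 1: 100 × (1 - 0) / 0 is undefined. With no replacement (2.7.3) it stays missing.
- A one-point worsening is +100% from 1, +50% from 2, +33% from 3 and +17% from 6. A move from 1 to 3 is 100 × 2/1 = +200%.

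**2. Effect of exclusion on the absolute-change scale.** Let q be the share at Baseline 0. The mean change in all patients is (1 - q) × (mean change if Baseline > 0) + q × (mean change if Baseline = 0). Assume, on a 0-3 sub-scale with 100 patients, a mean change of -1.2 if Baseline > 0 and of 0 to +0.3 if Baseline = 0. None of these values is in the SAP.
- q = 5%: 95 remain at -1.20; all patients 0.95 × (-1.2) + 0.05 × (0 to 0.3) = -1.14 to -1.125.
- q = 20%: 80 remain at -1.20; all patients -0.96 to -0.90.
- q = 40%: 60 remain at -1.20; all patients -0.72 to -0.60.

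**3. Mean percentage change when nothing truly changes.** Assume binomial scores (3, 6 or 30 points, probability p per point), the same distribution at both visits, and latent correlation 0.6. The share at 0 is (1 - p) to the power of the maximum score; for example 0.85³ = 61.4% and 0.60³ = 21.6%. Simulation gives:

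| Range | p | Baseline 0, dropped | Mean % change in the rest | Dropped patients later above 0 |
|---|---|---|---|---|
| 0-3 | 0.15 | 61% | -32% | 23% |
| 0-3 | 0.25 | 42% | -18% | 34% |
| 0-3 | 0.40 | 22% | -4% | 49% |
| 0-3 | 0.50 | 12.5% | +2% | 58% |
| 0-6 | 0.15 | 38% | -13% | 37% |
| 0-6 | 0.25 | 18% | +1% | 52% |
| 0-6 | 0.40 | 5% | +9% | 69% |
| 0-30 (total) | 0.15 to 0.40 | under 1% | +11% to +2% | not material |

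Mean absolute change in all patients is 0 in every row, and so is the median percentage change. Exclusion pulls the mean percentage down and small denominators push it up; which one wins depends on p.

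**4. The same model with a large assumed improvement.** With p = 0.25 at Baseline and 0.05 at follow-up on a 0-3 sub-scale, the mean percentage change in the included patients is -82.9%. The all-patient ratio of means is 100 × (0.15 - 0.75) / 0.75 = -80.0%. Across Baseline p of 0.25 to 0.50 the gap is about 2 to 3 percentage points, and 0.5% to 4% of the Baseline-0 patients rise above 0.

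**The case against.** A reader might infer that these patients vanish from the DLQI analysis, that worsening is hidden, and that the reported change is biased towards benefit. The documents do not support that.

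- **Exclusion is score by score.** A patient at 0 on Work and School stays in the change tables of every other score on which the Baseline is above 0, normally including the total.
- **Patients at 0 need not worsen.** They can also stay at 0.
- **Worsening remains visible elsewhere.** Absolute values of all seven scores by visit and the counts with DLQI 0 or 1 keep these patients. Section 2.7.1 names the score itself as the secondary variable. Section 2.1 requires by-patient listings, and it reports the number of observations and the median, so the reduced N will show.
- **No fixed direction of bias.** Percentage change has no all-patient value when Baseline can be 0, and step 3 shows the sign reversing. The larger distortions there assume no true change; step 4 shows a small gap if improvement is large.
- **Frequency is unknown.** The SAP gives no Baseline sub-scale data, so it cannot be said that zeros will be common.

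All of this stands and limits the point. It does not remove it. Visit means of absolute values do not pair each patient with their own Baseline, and under the observed-data rule the patients contributing can differ between visits. An absolute-change table also varies in membership, but it keeps the pairing. The 0/1 count does not separate a patient who reached 0 or 1 from one who started there, and it does not describe the sub-scales.

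**Conclusion.** The point holds for the sub-scales and is minor. From the text alone: percentage change is the only DLQI change summary, it is undefined at a Baseline of 0, 0 is a legitimate score, and no rule covers it. Affected patients therefore leave that score's change summary at every visit, and small denominators make the mean unstable for those who remain.

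The size rests on assumption. Under the binomial model with p of 0.15 to 0.40, a 0-3 sub-scale would lose 22% to 61% of patients and a 0-6 sub-scale 5% to 38%. The resulting distortion of the mean runs from about -32% to +9% across those sub-scales when nothing truly changes, and is about 2 to 3 percentage points under a large improvement. Exclusion hardly touches the total score. No hypothesis test is planned for the DLQI, and the co-primary conclusions on proSPI (s) and saSPI (s) are unaffected.

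**What to change.** In section 2.7.2, under DLQI:

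- Add absolute change from Baseline, in all patients with a Baseline and a visit value, as the change summary for all seven scores, as the section already does for saPASI.
- State that percentage change is not computed when the Baseline score is 0.
- For each score and visit, report the number excluded for that reason and how many of them have risen above 0.

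This costs a few lines of SAP wording and one derived variable. It needs no new data and leaves the other planned DLQI outputs as they are.

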2.7.3 Handling of missing values/censoring/discontinuations

Missing values for the secondary variable will not be replaced. Subjects with no post-Baseline value will be excluded from this analysis.

2.8 Safety analyses

Analysis of safety data will be on the SAF.

2.8.1 Adverse events (AEs)

AEs will be presented for the whole study period.

Only AEs that are treatment emergent are summarized. Treatment emergents are defined as events started after the first dose of study medication or events present prior to the first dose of study medication but increased in severity, frequency or clinical feature based on PT and started prior to end of study.

Treatment-emergent adverse events (TEAEs) will be included in all summaries and listings. AEs occurring after signing of informed consent but before first dose of study treatment and those occurring after study completion will be listed only. If any event has an incomplete onset date, this will be handled as described in [Appendix 5.1](#).

AEs will be coded by primary SOC and PT according to the MedDRA version 19.1 or later.

AEs will be summarized by presenting the number and percentage of patients having any AE, having an AE by SOC, and having an AE by PT. Summaries will also be presented for AEs by severity, study treatment related AEs, serious adverse events (SAEs), AE's leading to study drug discontinuation, and AE's leading to death.

Patients who experienced multiple AEs for a PT will be counted once, similarly for patients with multiple AEs per SOC. If a particular AE 'severity' is missing, this variable will be listed as missing and treated as missing in summaries. If a patient reports more than one AE with the same PT, only the greatest severity will be presented for this AE. If a patient reports more than one AE within the same primary SOC, the patient will be counted only once with the highest severity at the SOC level, where applicable.

For the legal requirements of clinicaltrials.gov and EudraCT, two required tables on TEAEs with an incidence greater than 5% and on treatment emergent SAEs and SAE suspected to be related to study treatment will be provided by SOC and PT on the SAF.

If for a same patient, several consecutive AEs (irrespective of study treatment causality, seriousness, and severity) occurred with the same SOC and PT:

- a single occurrence will be counted if there is ≤ 1 day gap between the end date of the preceding AE and the start date of the consecutive AE
- more than one occurrence will be counted if there is > 1 day gap between the end date of the preceding AE and the start date of the consecutive AE

For occurrence, the presence of at least one SAE / SAE suspected to be related to study treatment / non SAE has to be checked in a block e.g., among AE's in a ≤ 1 day gap block, if at least one SAE is occurring, then one occurrence is calculated for that SAE.

The number of deaths resulting from SAEs suspected to be related to study treatment and SAEs irrespective of study treatment relationship will be provided by SOC and PT.

A listing of all AEs will be presented. A column indicating if the AE is treatment emergent or not will be shown. Non-treatment emergent AEs will not be summarized; they will only be listed in final analysis.

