1.1 Study design

This is an open-label multicenter, single arm study in 120 patients with moderate to severe psoriasis. There will be no randomization nor interim analysis for this study.

[figure not shown]
The study consists of five epochs:

- Screening to occur between day -28 and day -7
- Treatment
 - Treatment period 1
 - Treatment period 2
- Extension treatment period
- Follow-up

There will be an initial induction phase (5 weekly injections) before switching to monthly injections until Week 16. The patient will continue with monthly injections until Week 48 in case of a favorable response to treatment at Week 16. Patients who are deemed to be benefiting from the study drug after 48 weeks of treatment could be continuously treated until 3 November 2016 or until commercialization of Cosentyx[®] in France, whichever occurs first.

An illustration of the study design is depicted in [Figure 1.1](#).

Figure 1-1 Study design

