1.2.2 Secondary objectives

Key secondary objectives are:

- ✓ to assess Psoriasis Area and Severity Index (PASI) weekly from week 0 to 4 then every 4 to 8 weeks until Week 56
- ✓ to evaluate correlation between PASI and proSPI (s)

Other secondary objectives include:

- ✓ to assess proSPI (s, p and i) over time (weekly from Week 0 to Week 4 then every 4 to 8 weeks until Week 56).
- ✓ to assess saSPI (s, p and i) over time (weekly from Week 0 to Week 4 then every 4 to 8 weeks until Week 56).
- ✓ to assess Dermatology Life Quality Index (DLQI) over time (weekly from Week 0 to Week 4 then every 4 to 8 weeks until Week 56).
- ✓ to assess self-administered PASI (saPASI) (weekly from Week 0 to Week 4 then every 4 to 8 weeks until Week 56).
- ✓ to assess pain, itching, and scaling using the Psoriasis Symptom Diary questionnaire over time (weekly from Week 0 to Week 4 then every 4 to 8 weeks until Week 56).

- to evaluate correlation between proSPI (for each component separately: s, p, i) and DLQI
- to evaluate correlation between proSPI (p, i separately) and PASI
- to evaluate safety during the treatment period (until the Week 52) and during the extension treatment period (after the Week 52)

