2.2 Analysis sets

The following analysis sets will be used in this study:

Included Set (IS): The included set will comprise all patients included in the study. A patient is considered to be included in the study if he/she successfully completes the screening period. Completion of screening period is defined as patient who has “Will the subject continue into the Treatment phase?” equal to “Yes” from the *Screening Phase Disposition* eCRF page.

Full Analysis Set (FAS): The FAS will comprise all patients in the IS who are administered with at least one dose of investigational drug with at least one Baseline and one post-Baseline SPI evaluation.

The primary analysis will be performed on the FAS.

Safety Analysis Set (SAF): The SAF will comprise all patients in the IS who are administered with at least one dose of investigational drug during the treatment period.

Per Protocol Set (PPS): The PPS will comprise all patients in the FAS without any major protocol deviation.

Analysis sets for specific outputs are given in [Table 2-2](#).

Table 2-2 Analysis data sets for specific outputs

Table	IS	FAS	SAF	PPS
Concomitant medication			x	
Demographics and Baseline characteristics	x			
Exposure			x	
Medical history	x			
Other efficacy analyses		x		
Patient disposition	x			
Patient reported outcomes		x		
Primary and key secondary efficacy variables		x		x
Protocol deviations	x			
Safety analyses			x	

The number and percentage of patients in each analysis set will be summarized based on the IS.

If protocol deviations (PDs) occur, then the data from specific patients, visits, or evaluations may be excluded from analysis. The criteria and determination of clinically significant PDs leading to exclusion from PPS will be finalized prior to DBL and analysis.

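### The safety objective is split at Week 52, but every planned AE table pools the whole study, so none gives the incidence in either period

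*SAP*

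**What the plan says.** Section 1.2.2 lists as a secondary objective "to evaluate safety during the treatment period (until the Week 52) and during the extension treatment period (after the Week 52". It names two periods and the boundary between them.

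Section 2.8.1 opens its AE plan with "AEs will be presented for the whole study period". The tables that follow are any AE, by SOC, by PT, by severity, treatment-related, serious, leading to discontinuation and leading to death. There are also registry outputs, described as "two required tables on TEAEs with an incidence greater than 5" percent and on serious events. None is by period. A patient is counted once per PT and once per SOC. For occurrences, "more than one occurrence will be counted if there is > 1 day gap" between consecutive events, again with no split at Week 52. The section also says "A listing of all AEs will be presented"; the only flag it names for that listing is treatment emergence.

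The denominator comes from Section 2.2: "The SAF will comprise all patients in the IS who are administered with at least one dose of investigational drug during the treatment period". No set is defined for patients treated in the extension. Section 1.1 says who they are: "Patients who are deemed to be benefiting from the study drug after 48 weeks of treatment could be continuously treated".

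**The concern.** The objective asks about safety in each of two periods, and the AE tables answer a different question: what happened at any time in the study. The extension population is selected for apparent benefit and is smaller than the Safety Analysis Set, so a percentage of the full set cannot stand in for incidence in the extension.

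The listing would let someone derive a split later. The cut-off rule and the denominator would then be settled with the data in view. The trial is single-arm with no planned safety test, so what is at stake is the description of safety by period and not the primary result.

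**Working it through.** The plan gives no figure to reproduce here. The check compares the objective with the planned outputs, then uses simple counts to show the consequence.

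**1. Which safety outputs can be read by period?**

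| Output (SAP section) | Split planned |
|---|---|
| Disposition (2.3.1) | By study period, on the Included Set |
| Laboratory data (2.8.3) | By visit |
| Vital signs (2.8.4.2) | Whole study, but summarised at each visit |
| AE tables (2.8.1) | None |
| AE listing (2.8.1) | None named; onset dates would allow one |

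The plan splits by period or visit elsewhere, so pooling is not its general convention. Section 4 changes only the objectives assessed until Week 56. The safety objective has no Week 56 limit, so Section 4 leaves it as it stands.

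**2. Can the period incidences be recovered from the pooled table?** Inputs: 120 patients (Section 3), all assumed to be in the Safety Analysis Set. The SAP does not give the number treated in the extension, so 40, 60 and 100 are assumed. Take a PT reported as 12/120 = 10.0%. Treatment-period incidence is the number with onset before Week 52 divided by 120; extension incidence is the number with onset after it divided by 40, 60 or 100.

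| Patients before / after Week 52 | Pooled | Treatment period | Extension (40 / 60 / 100) |
|---|---|---|---|
| 12 / 0 | 10.0% | 10.0% | 0% |
| 0 / 12 | 10.0% | 0% | 30% / 20% / 12% |
| 6 / 6, different patients | 10.0% | 5.0% | 15% / 10% / 6% |
| Same 12 in both, counted once | 10.0% | 10.0% | 30% / 20% / 12% |

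One pooled figure fits all four rows, so neither period's incidence can be recovered.

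**3. Do the exposure categories supply the extension denominator?** Section 2.4.1 defines duration as end of study date minus start date plus 1. A patient who ends at the scheduled Week 52 visit (Day 365, Table 2-1) has 365 days. Fifty-two weeks is 52 × 7 = 364 days, and 365/7 = 52.14 weeks. That patient falls in the category above 52 and up to 72 weeks without any extension treatment. The category therefore does not identify extension patients.

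**4. Is the cut-off already fixed?** Not operationally. Table 2-1 schedules Week 52 on Day 365 but gives it a window of Day 352 to Day 379, and the actual visit date may differ from both. An AE starting on Day 370 falls after the scheduled day but inside the window.

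**5. Effect on the registry table.** The threshold is an incidence greater than 5%. For a PT that starts only in the extension, on the same assumptions:

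- 6 patients: 6/120 = 5.0% pooled, so it does not enter. In the extension it is 6/40 = 15.0%, 6/60 = 10.0% or 6/100 = 6.0%.
- 7 patients: 7/120 = 5.8% pooled, so it enters. In the extension it is 7/40 = 17.5%, 7/60 = 11.7% or 7/100 = 7.0%.

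**The case against.** The objective can be read as scope only: follow safety through both periods, with no call for separate incidences. Whole-study tables would then suffice. That reading is possible but less natural, because the objective repeats the preposition for each period and states the boundary.

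The disposition table names the extension treatment period, so the number who entered it can probably be worked out from completers plus discontinuers. This stands as far as the count goes. But the table is on the Included Set, and no AE table uses that number as its denominator.

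The room for later choice is limited, since the objective fixes Week 52 and Table 2-1 gives Day 365. That is fair. What stays open is visit date, scheduled day or end of window, and where follow-up events go.

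The 6-patient example sits exactly on the 5% threshold, in a table that exists for registry requirements. The same PT still appears in the full SOC/PT table, and serious events, discontinuations and deaths have their own summaries. All of this stands: the example shows the mechanism and is not a forecast. Whether the protocol itself planned pooled AE tables cannot be seen from the SAP, so the mismatch is asserted only within the SAP.

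Finally, extension length varies by patient because treatment may run to a calendar date or to commercialization. Crude percentages by period would cover unequal follow-up. That is a reason to add exposure-adjusted rates, not to leave the split out.

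**Conclusion.** The concern holds. The SAP states a two-period safety objective and fixes an AE presentation that cannot answer it. It should be fixed before database lock.

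The gap covers the AE tables only. Laboratory and vital-sign data are by visit, disposition is by period, and every AE is listed. The primary analysis, alpha and sample size are unaffected.

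The size depends on how many patients are treated in the extension, which the SAP does not state. With 120 safety patients and 40 to 100 in the extension, a PT confined to the extension is understated in the pooled table by a factor of 120/40 = 3.0 down to 120/100 = 1.2. That the pooled tables cannot yield the period incidences does not depend on this assumption.

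**What to change.** In Section 2.8.1, keep the whole-study tables and add TEAE and SAE summaries (any, SOC, PT) by onset period:

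- **(a) First dose to Week 52**, with the Safety Analysis Set as denominator.
- **(b) After Week 52, during the extension treatment period**, with safety-set patients treated in the extension as denominator.

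Define the cut-off once, for example the Week 52 visit date, or Day 365 if that visit is missing. Events in follow-up, and events after Week 52 in patients who do not enter the extension, stay in the whole-study tables and the listing.

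For partial onset dates the SAP already says "If any event has an incomplete onset date, this will be handled as described in" Appendix 5.1. Use the imputed date from Appendix 5.1.1 to assign the period, and footnote the number of events whose known date parts fit both periods. Those rules separate events before and after first dose and were not written for a Week 52 boundary.

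Exposure-adjusted rates per period would be a useful addition, given the variable extension length.

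If the split is not wanted, say so in Section 4 as a change to the safety objective.

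The cost is SAP wording, one period flag and two further runs of existing AE tables, or a single sentence in Section 4. No new data are needed.

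### SAP Section 2.8.1 pools adverse events over the whole study as patient percentages with no allowance for time at risk, although follow-up varies by design and the safety objective is set separately until and after Week 52

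*SAP*

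**What the plan says.** **How AEs are summarized.** SAP Section 2.8.1 sets the reporting period: "AEs will be presented for the whole study period". It sets the measure: "AEs will be summarized by presenting the number and percentage of patients having any AE", then by SOC and by PT. It sets the counting rule: "Patients who experienced multiple AEs for a PT will be counted once, similarly for patients with multiple AEs per SOC". The further summaries (severity, related, serious, leading to discontinuation, leading to death) name no other measure.

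**Registry tables.** The same section plans "two required tables on TEAEs with an incidence greater than 5" per cent, and treatment-emergent SAEs. Recurrences are also counted here: "more than one occurrence will be counted if there is" a gap of more than one day. These counts have no person-time denominator either.

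**Follow-up.** Section 1.1 states: "The patient will continue with monthly injections until Week 48 in case of a favorable response to treatment at Week 16". Patients judged to benefit after 48 weeks "could be continuously treated until 3 November 2016 or until commercialization of Cosentyx" in France, whichever comes first.

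**Exposure.** Section 2.4.1 defines duration from first dose to end of study and tabulates it in five bands, from 4 weeks or less to more than 72 weeks. Section 2.8.1 does not use it.

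**Objective.** Section 1.2.2 lists safety during the treatment period, to Week 52, and during the extension, after Week 52, as two periods to evaluate.

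**The concern.** A patient watched for longer has more opportunity to report a first event. When follow-up differs widely between patients, the percentage with at least one event mixes how often events occur with how long patients were observed. Here three design rules, together with drop-out (20 of 120 anticipated in Section 3), make the durations unequal, and the length of the extension depends partly on when a patient enrolled.

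With no control arm, the AE figures can be read only on their own or against outside data. A reader who sets a pooled percentage beside a 52-week figure from elsewhere cannot tell whether a difference comes from the drug or from the follow-up. Pooling also means that no AE table answers the objective as Section 1.2.2 words it, in two periods.

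**Working it through.** **Inputs from the SAP.** 120 patients and an anticipated drop-out of 20 (Sections 1.1 and 3); continuation gates at Week 16 and after 48 weeks, and the calendar or commercialization stop (Section 1.1); exposure bands (Section 2.4.1); a 5% cut for the registry tables (Section 2.8.1). The SAP states no AE rate, so it has no figure of its own to reproduce here.

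**Assumed, for illustration only.** A constant rate *r* of first events, a year of 52 weeks, and three follow-up mixes for 120 patients:

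- A: 100 followed 80 weeks, 20 followed 16 weeks
- B: 100 followed 52 weeks, 20 followed 16 weeks
- C: 60 followed 52 weeks, 40 followed 16 weeks, 20 followed 4 weeks

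**Step 1: chance of at least one event by week *w*.** P(*w*) = 1 − exp(−*r* × *w*/52).

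| Rate per patient-year | 4 wk | 16 wk | 52 wk | 72 wk | 80 wk |
|---|---|---|---|---|---|
| 0.05 | 0.4% | 1.5% | 4.9% | 6.7% | 7.4% |
| 0.20 | 1.5% | 6.0% | 18.1% | 24.2% | 26.5% |

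**Step 2: pooled percentage in each mix, at 0.05.**

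- A: (100 × 0.0740 + 20 × 0.0153)/120 = 7.71/120 = 6.4%
- B: (100 × 0.0488 + 20 × 0.0153)/120 = 5.18/120 = 4.3%
- C: (60 × 0.0488 + 40 × 0.0153 + 20 × 0.0038)/120 = 3.61/120 = 3.0%

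At 0.20 the same steps give 23.1%, 16.1% and 11.3%.

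**Step 3: first events per 100 patient-years.** Under a constant hazard the expected time to first event or end of follow-up is P(*w*)/*r* per patient. At 0.05 the patient-years are 154.2 (A), 103.6 (B) and 72.3 (C). Each mix returns 5 per 100 patient-years, for example 7.71/154.2. The constant-hazard assumption guarantees this result, so it does not show that the rate is always free of the follow-up mix.

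**Step 4: what a period split does.** A and B are the same trial up to Week 52: 100 patients reach it and 20 leave at Week 16. At 0.05, the percentage until Week 52 is therefore 4.3% in both. The difference lies wholly in the extension, where A has 100 patients observed for 28 more weeks: 1 − exp(−0.05 × 28/52) = 2.7% of those entering. In C, attrition before Week 52 still lowers the percentage, to 3.0%.

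**Step 5: where the rate also fails.** Suppose the hazard is 0.20 until Week 16 and 0.05 afterwards. By Week 16, 5.97% have an event, at 0.2984 patient-years each. Beyond Week 16, the extra events per patient are 0.9403 × [1 − exp(−0.05 × 64/52)] = 0.0561 for 80 weeks and 0.9403 × [1 − exp(−0.05 × 36/52)] = 0.0320 for 52 weeks. Dividing by 0.05 gives 1.122 and 0.640 extra patient-years.

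- A: 12.77 events in 148.1 patient-years = 8.6 per 100; percentage 12.77/120 = 10.6%
- B: 10.36 events in 99.8 patient-years = 10.4 per 100; percentage 10.36/120 = 8.6%

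The longer mix now has the higher percentage and the lower overall rate. Neither measure is sufficient alone. Until Week 52, A and B again agree on both, at 8.6% and 10.4 per 100.

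**The case against.** The case for leaving the plan alone is substantial. The study has one arm, no safety hypothesis and no stated benchmark, so unequal follow-up cannot bias a comparison between arms. The crude percentage has a clear meaning: the share of treated patients who had an event while observed. Duration is not hidden, since Section 2.4.1 tabulates exposure on the same safety set and all AEs are listed. The exposure bands are table bins and do not prove that durations will spread that far. All of this stands, and it limits the point to an improvement in presentation and interpretation.

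Three stronger readings are tempting, and the SAP does not support them.

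- A reader might infer that the percentages make the drug look safer. There is no reference against which this could be judged: early stopping lowers the pooled figure, while including the extension raises it relative to a 52-week figure.
- A reader might infer that a period split would not help, because extension length varies with enrolment. Section 1.1 states the calendar stop only for treatment after 48 weeks, so a split largely removes enrolment timing from the figures until Week 52 (step 4).
- A reader might infer that rates should replace percentages. Step 5 shows that rates, too, depend on the follow-up mix when the hazard changes or when those who stay differ from those who leave.

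Two things remain. No AE summary takes account of time at risk, and none is split into the two periods that the objective names.

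**Conclusion.** The point holds as a recommended change. Section 2.8.1 fixes a pooled percentage that depends on the follow-up mix and does not deliver the two-period safety objective in Section 1.2.2. That mismatch rests on the text alone and needs no assumption.

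The size of the dependence cannot be determined from the SAP, which gives neither event rates nor enrolment dates. The spread from 3.0% to 6.4% at 5 per 100 patient-years shows what is possible under assumed mixes and a constant hazard; it does not predict this trial's result. It can straddle the 5% cut, but that cut is stated for the registry tables only. The main SOC and PT summaries have no stated cut, so no event would be lost from them, and the fix leaves the registry tables as they are.

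**What to change.** In Section 2.8.1:

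1. Keep the n (%) tables for the whole study and the registry tables.
2. Add TEAE tables for the period until Week 52 and for the extension after Week 52, each with the patients entering that period as denominator.
3. Beside n (%), by period and overall, give patients with a first event per 100 patient-years with an exact Poisson 95% confidence interval. Time runs from first dose, or from the start of the period, to the first event or the end of study as used in Section 2.4.1 (for the first period, no later than Week 52). That section ends exposure at the last visit of the treatment period for patients who discontinue, so state that events and time are counted to the same date.
4. Do this for any TEAE, SAEs, related AEs, AEs leading to discontinuation, and each SOC and PT.
5. State that rates and percentages are read together, and that the rates assume a roughly constant hazard within each period.

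The cost is small. The dates needed are already specified (Section 2.4.1 and Appendix 5.1.1), and neither data collection nor study conduct changes. The downsides are extra columns, wide intervals for rare terms with about 120 patients, and the constant-hazard assumption, which the period split relaxes but does not remove.
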